Methods and analysis: Prospective cohort in seven Chilean ICUs with a qualitative component. Sample: 450 adults, able to walk independently, in ICU and mechanical ventilation >48 hours with and without COVID-19. Assessments: Only at ICU discharge, Clinical Frailty Scale, Charlson comorbidity index, mobility (FSS-ICU) and muscle strength (MRC-SS). Cognitive functioning (MOCA-blind), anxiety and depression (HADS), post-traumatic stress (IES-R) symptoms, disability (WHODAS 2.0), quality of life (EQ-5D-3L), employment, and survival will be assessed at ICU discharge, 3 and 6 months. Physical activity (GPAQ and actigraphy) will be measured in a sample at 6 months after ICU discharge. The perceptions of family members regarding the ICU stay and the later recovery will be explored 3 months after discharge. Health care professionals will be invited to discuss the challenges faced during the pandemic using semi-structured interviews.

Ethics and dissemination: The “Impact on Mental, Physical, And, Cognitive functioning of Critical care Time due to COVID-19” (IMPACCT-COVID19) study was approved by the local Research and Clinical Trials Unit, the local Ethics Committee (2020-78) and each participating site. All eligible patients will receive

verbal and written information about the study before signing an informed consent form. A leaflet containing information about post-intensive care syndrome and rehabilitation alternatives will be provided to all participants. Study findings will be published in peer-reviewed journals following standard guidelines and disseminated through social media and conference meetings.

Keywords: COVID-19, critical care, postintensive care syndrome, rehabilitation, follow-up studies

Strengths and limitations of this study:

- The mental, physical and cognitive consequences related to the post-intensive care syndrome could be greater in periods of high occupancy during the pandemic and even more in patients infected with COVID-19.
- This is the first Chilean multicentre follow-up study assessing functional outcomes of mechanically ventilated patients discharged from intensive care unit (ICU).
- This study will also explore the views and experiences of family members/next of kin and health care professionals working during the pandemic.

INTRODUCTION

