Post-intensive care syndrome (PICS) is a common consequence of an intensive care unit (ICU) stay and can last up to 5 years.[1–3] The family members are often affected, reporting diminished quality of life and mental health related quality of life.[4] About 80% of family members become informal carers and 33% of families

see a significant reduction of income the first 6 months after discharge.[5] The extent to which these problems will be modified by the pandemic and coronavirus disease 2019 (COVID-19) remains unknown.

If under normal circumstances, an ICU stay has detrimental effects, the pandemic added two extra factors. Firstly, a rapid and exponential increase in acute care bed capacity might have affected the quality of care delivered by spreading too thin highly skilled healthcare staff. Secondly, COVID-19 involves a new disease with great uncertainties regarding treatment, prognosis and long-term effects. Early reports suggest that 64% of patients who were discharged from ICU after severe COVID-19 have at least one symptom of PICS at 6 months after discharge[6] and 32% had anxiety or depression symptoms,[7] which suggests these patients will have similar impairments to what has been reported for other ICU survivors previously.[8,9] Additionally, infection control protocols meant that healthcare staff had to wear personal protective equipment and family visiting was restricted.[10] These factors add another layer of potential negative effects due to challenges in communication with patients and their family members. Therefore, we hypothesize that the prevalence and severity of mental, physical, and cognitive impairments will be higher in patients treated in periods of higher bed occupancy and those who had severe COVID-19. In the case of family members, we expect that the experience of having a next of kin in the ICU during pandemic would be stressful and traumatic, but those with social support will cope better. In the case of staff members, their experiences will vary greatly depending on their profession and workplace, but we expect places with a more open/ less hierarchical structure to have coped better with the increase in demand.

The primary objective of this study is to compare the trajectory of mental, physical and cognitive impairments at ICU discharge, 3 and 6 months of mechanically ventilated adult patients who survived an ICU stay due to severe COVID-19 or other causes, during the pandemic. Secondary objectives are:

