- To compare the disability, quality of life and survival rate at ICU discharge, 3 and 6 months of patients who were admitted to ICU due to severe COVID-19 or other causes during high and low bed occupancy in the pandemic;
- To describe the sedentary behaviour and physical activity levels in a sample of ICU survivors during the COVID-19 pandemic using a one-week actigraphy protocol;
- To explore the psychological and emotional experiences reported by family members/next of kin of patients admitted to the ICU during the COVID-19 pandemic;
- To explore the emotional, intellectual, physical and administrative challenges faced by the participating ICU staff during the COVID-19 pandemic;
- To evaluate the feasibility of the follow-up from ICU discharge to 3 and 6 months during the pandemic.

METHODS

Study design and setting

The “Impact on Mental, Physical, And, Cognitive functioning of Critical care Time due to COVID-19” (IMPACCT-COVID19) is a prospective, multicentre, cohort study in seven Chilean academic medical-surgical ICUs. This study also involves a

qualitative component including semi-structured interviews with family members/next of kin of ICU survivors and with ICU staff from the participating centres. Participating sites are four public and three private hospitals comprising a pooled bed capacity of about 200 ICU beds for both COVID-19 patients and patients admitted for other causes. The IMPACCT-COVID19 study started in October 2020. Data collection is planned until November 2021 to achieve completion of the study in February 2022.

Study population and eligibility criteria

Adult patients (≥ 18 years old) who are mechanically ventilated for at least 48 hours in one of the participating ICUs and do not meet any of the exclusion criteria (**Table 1**) will be invited to participate.

Table 1. Exclusion and stopping follow-up criteria

Exclusion criteria	Rationale
Unable to walk independently 2 weeks prior to ICU admission (with or without a gait aid)	Potential confounding factor
S5q < 5 or CAM-ICU positive within 72 hours after ICU discharge	Unable to evaluate
Patient who do not understand or speak Spanish	Unable to evaluate
Patient unable to communicate verbally	Incomplete assessment data
Burn or severe trauma as admission diagnosis	Incomplete assessment data
Any neurological disorder (i.e. spinal cord injury, stroke and brain tumours) as admission diagnosis	Potential confounding factor

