Transferred to a non-participating study centre before ICU discharge assessment	Unable to evaluate
Recent prolonged hospital stay (extended by more than 3 months)	Potential confounding factor
Criteria to stop follow-up	
Re-admission after being ICU discharged	Potential confounding factor
Withdrawal of consent	Incomplete assessment data
Death before 3 or 6 months from ICU discharge	Incomplete assessment data

ICU, intensive care unit; s5q, simple 5 questions scale; CAM-ICU, Confusion Assessment Method for the Intensive Care Unit

Procedure

The planned flow of participants throughout the study is presented in **Figure 1**.

Daily, patients will be screened to identify those who could potentially be discharged from the ICU. Each site coordinator, which is a clinician physiotherapist responsible for the site, will check that the patient is delirium-free (CAM-ICU negative) and cooperative (i.e. using 5 standardised questions: open [close] your eyes; look at me; open your mouth and stick out your tongue; nod your head; raise your eyebrows when I have counted up to five[11]) within 72 hours from ICU discharge. Every patient deemed eligible will be invited to participate and will receive verbal and written information about the study. Patients will be assessed at ICU discharge (T1, defined by the point between medical decision of discharge until 72 hours after), 3 months (T2) and 6 months after ICU discharge (T3). Fifty-eight physiotherapists were trained for the assessments at ICU discharge, which included in-person measurements and self-administered questionnaires. Physiotherapists had to be working in one of the participating ICUs at the time of the training. Training for standardising T1 assessments was delivered by experienced physiotherapists and researchers (ACM, CMO and FGS). For the follow-up assessments (T2 and T3), patients will be contacted via email or telephone to schedule a phone call evaluation performed by trained interviewers.

Baseline data collection

After the patient agreed to participate and signed the informed consent form, the following baseline data will be collected from the patient clinical records: age, gender, body mass index (BMI), highest educational level achieved (no formal

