education, primary school, secondary school, undergraduate or postgraduate), admission diagnosis, Charlson Comorbidity Index, duration of mechanical ventilation, length of hospital stay before ICU admission, ICU length of stay, number of intubations and the maximum level of organ system support received.[12]

Measurement Outcomes

The assessment points and measurement instruments are presented in **Table 2**. Measurement instruments were selected according to the recommended Core Outcome Measurement Set for critical illness survivors.[13,14]

Table 2. Schedule of enrolment and follow-up of the IMPACCT-COVID19 study

	Study period		
	Enrolment		Follow-up
	ICU	3 months from enrolment	6 months from enrolment
Eligibility screening			
Inclusion and exclusion	X		
Invitation to participate			
Informed consent	X		
Patient characteristics			
Age, gender, BMI	X		
Data related to hospitalisation			
Diagnosis, MV days, ICU LOS	X		
Maximum level of organ system support	X		
Pre-admission health and functioning			
Charlson Comorbidity Index	X		
Educational level	X		
Employment status	X	X	X
Clinical Frailty Scale	X	X	X
Physical functioning			
MRC Sum Score	X		
FSS-ICU	X		
Cognitive functioning			
MoCA blind	X	X	X

Mental functioning			
IES-R	X	X	X
HADS	X	X	X
Disability and quality of life			
WHODAS 2.0	X	X	X
EQ-5D-3L		X	X
Sedentary behaviour and physical activity			
Actigraphy			X
GPAQ			X
Survival rate	X	X	X

ICU, intensive care unit; BMI, body mass index; MV, mechanical ventilation; LOS, length of stay; FSS-ICU, Functional Status Score for the Intensive Care Unit; MRC, Medical Research Council; MoCA, Montreal Cognitive Assessment; IES-R, Impact of Event Scale Revised; HADS, Hospital Anxiety and Depression Scale; WHODAS, World Health Organization Disability Assessment Schedule; EQ-5D-3L, European Quality of Life Health Questionnaire 5 domains; GPAQ, Global Physical Activity Questionnaire

When available, we used the Chilean version of each instrument, otherwise, the validated version in Spanish. Trained physiotherapists will take an estimated maximum time of 70 minutes to perform the assessment at ICU discharge (T1). A trained interviewer will take an estimated maximum time of 20 minutes to apply the questionnaires by telephone at 3 (T2) and 6 months (T3) after ICU discharge.

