Hodgson et al (2017) found that a quarter of ICU survivors had severe or moderate disability at 6 months after discharge, and half of them had mild disability.[8] There is no information to estimate how much the prevalence of disability increases during a pandemic; however, the prevalence of mental health issues could be used as a proxy of the expected impact on physical health. Hodgson et al (2017) found that 22% of patients had anxiety or depressive symptoms at 6 months after discharge. Lee et al (2007) found that among survivors of the SARS outbreak, 40% had at least moderate anxiety one year after.[42] This is equivalent to a relative risk of 1.81. Considering that measurement time points are different, we have estimated our sample size assuming a relative risk (RR) of 1.5 or 1.6, which is more conservative than the estimation based on the literature. The different scenarios used for the sample size calculation appear in **Table 3**.

Table 3. Different plausible scenarios for sample size calculation

Outcome	Risk in non-pandemic situation	Risk during the pandemic	Type 1 error	Power	Sample size
WHODAS 2.0	25% severe or moderate disability	40% severe or moderate disability (RR=1.6)	0.05	0.8	343

WHODAS 2.0	40% some degree of disability	64% some degree of disability (RR=1.6)	0.05	0.8	288
WHODAS 2.0	50% mild disability	75% mild disability (RR=1.5)	0.05	0.8	388
HADS	22% anxiety or depressive symptoms	40% moderate anxiety (RR=1.8)	0.05	0.8	226

HADS, Hospital Anxiety and Depression Scale; WHODAS, World Health Organization Disability Assessment Schedule; RR, relative risk

The most plausible scenario is that 40% of ICU survivors discharged in a low demand period will have some degree of disability and this will increase to 64% for those discharged during high-demand periods. Considering loss to follow-up, we estimate 550 patients need to be recruited at ICU discharge; so 413 patients are assessed at 3 months after discharge (25% loss to follow-up) and 289 patients at 6 months (30% lost to follow-up).

Quantitative analysis

Categorical variables will be presented as absolute and relative frequencies for each subgroup (i.e. admission diagnosis and treatment centre) and time point (i.e. ICU discharge, 3 and 6 months follow-up). In the case of normally distributed continuous variables, these will be summarised using the mean and standard deviation, while for those non-normally distributed, the median and interquartile range will be used instead.

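### The only stated power is for low- versus high-demand periods, not for the primary objective's COVID-19 versus other-causes comparison; occupancy is undefined and the longitudinal model names no exposure or covariates

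*Combined protocol and SAP*

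**What the plan says.** All references are to the combined protocol and SAP.

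- **Introduction, primary objective.** Trajectories of mental, physical and cognitive impairment are compared in ventilated patients "who survived an ICU stay due to severe COVID-19 or other causes, during the pandemic".
- **Introduction, hypothesis.** Impairments "will be higher in patients treated in periods of higher bed occupancy and those who had severe COVID-19".
- **First secondary objective.** Disability, quality of life and survival are compared in "patients who were admitted to ICU due to severe COVID-19 or other causes during high and low bed occupancy in the pandemic".
- **Measurement Outcomes.** The primary outcome is WHODAS 2.0 disability at 6 months.
- **Sample size calculation.** Patients discharged from October 2020 to April 2021 are invited. The preferred scenario is 40% with some disability in a low-demand period, and "this will increase to 64% for those discharged during high-demand periods". Table 3 gives 288 patients for these rates (alpha 0.05, power 0.8) under column headings that contrast a non-pandemic situation with the pandemic. The target of 550 recruited allows for losses.
- **Abstract.** The size differs: "Sample: 450 adults, able to walk independently".
- **Baseline data collection.** The list includes "age, gender, body mass index (BMI), highest educational level achieved" and "admission diagnosis, Charlson Comorbidity Index, duration of mechanical ventilation". Neither it nor Table 2 has an item for occupancy or demand period.
- **Quantitative analysis.** Descriptive subgroups are admission diagnosis and centre. Trajectories use longitudinal multilevel regression with robust standard errors for the seven centres. COVID-19 versus other causes is a named comparison only in the Cox survival model.

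**The concern.** A power statement is useful only for the contrast that will be tested. Here it is attached to a demand-period contrast for which no analysis is written, while the declared primary comparison has no stated power. The first secondary objective promises a high/low occupancy comparison without an exposure variable.

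The COVID-19 comparison is not randomised. The two groups may differ in age, comorbidity and the occupancy they met, and the plan does not say how these will be separated. Occupancy is a site-and-date variable and could be obtained later. Its cut-off, its time window and the model terms would then be chosen with outcomes in hand. Two analysts could follow this plan, report different contrasts with different covariates, and both claim to have complied.

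**Working it through.** **1. Contrasts side by side**

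| Place | Contrast |
|---|---|
| Primary objective | COVID-19 vs other causes |
| Hypothesis | Occupancy, and COVID-19 status |
| First secondary objective | COVID-19 vs other causes, and high vs low occupancy |
| Sample-size text | Low- vs high-demand period (40% vs 64%) |
| Table 3 | Non-pandemic vs pandemic (same rates) |
| Longitudinal model | None written |
| Cox model | COVID-19 vs other causes |

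The enrolment window rules out a non-pandemic group. Disability, the primary outcome, is named in the first secondary objective and not in the primary one.

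**2. The plan's own figures**

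The attrition chain reproduces: 550 × 0.75 = 412.5 (413), and 413 × 0.70 = 289.

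The 288 does not reproduce at 1:1. With p1 = 0.40, p2 = 0.64 and mean p̄ = 0.52:

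n per group = [1.96√(2p̄(1−p̄)) + 0.842√(p1(1−p1) + p2(1−p2))]² / (p2−p1)² = (1.385 + 0.577)² / 0.24² = 66.8, so 67 per group and 134 in total (150 with continuity correction).

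A total near 288 needs about 13-15% of patients in one group, a split the plan does not state. The present point does not rest on this, but it shows that the split matters.

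**3. Power if the figures are borrowed for COVID-19 vs other causes**

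The documents give neither the COVID-19 split nor disability rates by COVID-19 status, so both are assumed. The lower-risk group is set at 40%, with two-sided 0.05 and no clustering.

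Power = Φ[(p2−p1 − 1.96·s0)/s1], where s0 = √(p̄(1−p̄)(1/n1+1/n2)), p̄ is the size-weighted mean of p1 and p2, and s1 = √(p1(1−p1)/n1 + p2(1−p2)/n2).

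Example: 289 split 50:50 (144.5 each), relative risk 1.41. Then p2 = 0.564, p̄ = 0.482, 1.96·s0 = 0.1152, s1 = 0.0580, and (0.164 − 0.1152)/0.0580 = 0.841, which is 80% power.

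| | 50:50 | 70:30 | 80:20 | 90:10 |
|---|---|---|---|---|
| 289: power, RR 1.6 | 99% | 97% | 91% | 70-71% |
| 289: power, RR 1.4 | 78% | 71% | 59% | 37-38% |
| 289: RR detectable at 80% power | 1.41 | 1.45 | 1.51 | 1.66-1.67 |
| 236: power, RR 1.6 | 96% | 93% | 85% | 61-62% |
| 236: RR detectable at 80% power | 1.45 | 1.49 | 1.56 | 1.73-1.74 |

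Ranges show either group as the larger one. The 236 is 450 × 0.75 × 0.70 = 236.25, the abstract's size under the same losses.

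**4. Precision of the occupancy contrast**

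Patients in the same site and period share the same occupancy value. Suppose occupancy did not vary within a site and the seven sites were equal in size. The mean is 289/7 = 41.3 per site, and the design effect is 1 + 40.3 × ICC. For assumed intra-site correlations of 0.01, 0.02 and 0.05 it is 1.40, 1.81 and 3.01, leaving an effective 206, 160 and 96. With a site-size coefficient of variation of 0.5 (assumed), the design effect is 1 + (1.25 × 41.3 − 1) × ICC, leaving about 192, 144 and 82.

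**The case against.** The strongest reply is that COVID-19 is plainly the intended exposure. The primary objective says so, admission diagnosis is collected and is a descriptive subgroup, and the Cox model names it. That stands as to intent. It does not settle the exposure-by-time term, the covariates or the power.

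Occupancy is also not foreign to the team. Setting gives a pooled capacity of about 200 ICU beds, and staff interviews start once occupancy is back to usual. Neither defines high or low. The background remark that "a rapid and exponential increase in acute care bed capacity might have affected the quality of care delivered" is general and does not report these sites' capacity, but it is a reason to state the denominator.

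Several stronger readings are tempting, and the documents do not support them:

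- **The COVID-19 comparison is unadjusted.** The plan is silent on covariates. Some Table 1 exclusions are there to limit confounding, and centre is in the model. The defensible statement is that adjustment is not specified.
- **The SARS-outbreak figure is a further competing contrast.** It is a disclosed proxy for effect size, used with a more conservative relative risk. Only the text and Table 3 labels conflict.
- **There are three rival occupancy windows.** The hypothesis speaks of treatment, the secondary objective of admission and the sample-size text of discharge. This may be loose wording, since discharge also matches the enrolment rule. The gap is the missing definition.
- **The objective and outcome are unrelated.** WHODAS includes cognition and mobility, so they overlap. The mismatch is one of naming.

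Restating power will not change enrolment, which the funding window fixes. That limb corrects the report of what the study can detect.

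**Conclusion.** The point holds. The stated 80% power is not for the primary objective's contrast. High versus low occupancy has no definition, listed data item or written analysis. The longitudinal model names no exposure, exposure-by-time term or covariates. These gaps should be closed before outcomes are analysed.

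A reader might infer that the study is underpowered. The documents do not show that. If 40% versus 64% applied to COVID-19 status, power with 289 assessed would be 91% or more up to an 80:20 split and 70-71% at 90:10. With smaller effects or a more uneven split it would be lower. Every split and every COVID-19 effect here is an assumption, and the calculation is a binary comparison at one time without clustering, which is simpler than the planned longitudinal model.

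The effective numbers for the occupancy contrast are not an upper bound on the loss in general. They assume equal sites, and unequal sites leave fewer.

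**What to change.** 1. **Contrast and power.** Declare COVID-19 versus other causes as the primary contrast for 6-month WHODAS, and name disability in the primary objective. Give Table 3 and the sample-size text one contrast label. Restate the power or detectable relative risk for the declared contrast over stated splits, as tabulated above. Reconcile 450 and 550 into one recruitment target.
2. **Occupancy.** Before outcomes are analysed, define the measure, the bed denominator, the cut-off and one time window that does not depend on length of stay (for example, occupancy at ICU admission). Obtain it per site and date. Write the analysis for the first secondary objective, stating whether it means two separate contrasts or four groups.
3. **Model.** Write out the longitudinal WHODAS model with COVID-19 status, time and their interaction, taking the 6-month contrast as primary. Adjust for pre-ICU variables already collected: age, gender, BMI, education, Charlson index and the ICU-discharge Clinical Frailty rating, which refers to pre-illness status. Report the unadjusted result alongside. Occupancy belongs in the secondary-objective model; adding it to the primary model is a debatable choice, best kept as an optional sensitivity analysis.

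**Cost.** A data request to seven sites, which assumes that dated occupancy records exist (the documents do not mention any), plus extra model terms. No added patients. The restated power may be less favourable than 80%, and the occupancy contrast will be less precise than the patient count suggests.
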